**As per Protocol Amendment 3:**

For ongoing subjects, the next planned visit will be a Final/Withdrawal Visit, which will be the last visit with data collection. For new subjects that roll-over from (parent) trial TMC125-C234 (IMPAACT P1090), the next planned visit will be a Baseline Visit which will be performed per local standard of care and documented in the subject's medical records only.

For all new and ongoing subjects, all subsequent visits and assessments will be performed per local standard of care and documented in the subject's medical records only. Investigators will continue to report SAEs possibly related to ETR and pregnancies to the sponsor using regular pharmacovigilance reporting. This information will only be entered in the company safety repository.

For all new and ongoing subjects, if the subject exits the trial, the last visit will be a local standard of care visit but without dispensation of investigational medication.

Treatment will be continued until one of the following criteria is met: the investigator determines that the subject no longer benefits from ETR treatment (e.g., based on viral load); treatment limiting toxicity; loss to follow-up; patient withdrawal of consent; pregnancy; termination of the program by the sponsor; an ETR-based treatment regimen becomes commercially available for the subject's indication and is reimbursed, or can be accessed

through another source (e.g. access program, government program) in the region the subject is living in, or subjects can be switched to local standard of care, as appropriate.

Details on the timing of the treatment and assessments are given in the flowchart (see Section 2).

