### **5.2.5 REMOVAL OF SUBJECTS FROM THERAPY OR ASSESSMENT**

Subjects **may** be withdrawn from the trial if:

1. a SAE occurs;
2. they fail to comply with the protocol requirements or to cooperate with the investigator;
3. a grade 3 AE (with the exception of skin events / allergic reaction) occurs according to the DAIDS grading scale. Exceptions (unless clinical assessment foresees an immediate health risk to the subject) are:
  - subjects with pre-existing diabetes who experience a glucose elevation of grade 3;
  - subjects who experience a glucose, triglyceride or cholesterol elevation of grade 3 under non-fasted conditions;
  - subjects who experience asymptomatic glucose, triglyceride or cholesterol elevations of grade 3;
  - subjects who experience asymptomatic pancreatic amylase elevations of grade 3 with no past or active history of pancreatitis;
  - subjects who experience a grade 3 AE that is considered not related or doubtfully related to the study medication;
  - subjects who experience grade 3 absolute neutrophil count or asymptomatic grade 3 platelets.

Subjects **must** be withdrawn from the trial if:

1. the parent(s) or legal representative(s) withdraws consent for a pediatric subject, or the subject withdraws consent or assent;
2. the investigator considers, for safety reasons, it is in the best interest of the subject that he or she is withdrawn;
3. they experience a grade 4 AE or grade 4 laboratory toxicity considered at least possibly related to ETR by the investigator;
4. they experience a grade 3 or higher rash;
5. they experience a grade 3 or higher allergic reaction;

6. they develop clinical hepatitis;
7. pregnancy has been determined.
8. they can be switched to locally available ETR-based treatment regimens (ie, commercially available and reimbursed, or accessible through another source [eg, access program or government program]) or to local standard of care, as appropriate.

The date and the reason for discontinuation must be noted on the Case Report Form (CRF). If consent/assent is not withdrawn, all subjects prematurely discontinuing the trial must be seen for a follow-up visit, if they are not continuing treatment with ETR. The Trial Termination Section of the CRF is to be completed.

**As per Protocol Amendment 3**, study termination will be documented in the subject's medical records and recorded on a separate, paper termination disposition form to be shared with the sponsor.

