## 5.5 Safety Management Guidelines for Cutaneous Events

Toxicity management is at the discretion of the investigator, and is to take into account the protocol-defined procedures defined under 5.5.1 and 5.5.2, and the local standard clinical practice.

After termination of data collection (see Figure 1), toxicity management will be performed per local standard of care and documented in the subject's medical records only.

Clinical data in adults have shown that ETR is generally safe and well tolerated. As rash is a known class effect with NNRTIs, cutaneous events as described below have been closely monitored in trials with ETR. Rash events with ETR are now well characterized based on the large safety dataset from our double-blind placebo-controlled trials. This section describes the guidelines for management of rash and acute allergic reactions.

In general, all other AEs that are ongoing at the end of the treatment period should be followed up until satisfactory clinical resolution or stabilization at the investigator's discretion as per the local standard clinical practice.

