### 5.5.1 RASH MANAGEMENT

#### **Rash**

In case of rash, visits and assessments should be performed as described below and in the "Visit Schedule for Rash Management in Pediatric Patients" (see Section 7.4, Attachment 4) and "Visit Schedule for Rash Management in Adult Patients" (see Section 7.5, Attachment 5). Unscheduled follow-up visits for close follow-up of rash will be performed based on the grade (severity) of the rash. At the investigator's discretion, additional visits and assessments can be performed.

Dermatologist fees for evaluating subjects who experience a rash will be reimbursed by the sponsor.

The following grades are based on the DAIDS grading table (see Section 7.2, Attachment 2), with adaptations made by the sponsor.

**Subjects (and/or their legally acceptable representative) should be informed that they should contact their doctor and visit the clinic immediately when they notice any rash.**

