#### **Grade 1 and 2 Cutaneous Reaction/Rash**

A grade 1 cutaneous reaction/rash is defined as localized macular rash.

A grade 2 cutaneous reaction/rash is defined as diffuse macular, maculopapular, or morbilliform rash or target lesions.

Subjects experiencing a grade 1 or 2 rash or cutaneous event may continue treatment or have their trial medication interrupted at the investigator's discretion. Local safety sampling at the time of the rash and clinical follow-up for these AEs will be at the discretion of the investigator, however, close clinical follow-up is recommended to monitor for any progression of the AE.

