#### **Grade 3 or 4 Cutaneous Reaction/Rash**

A grade 3 cutaneous reaction/rash is defined as:

- Diffuse macular, maculo-papular, or morbilliform rash with vesicles or limited number of bullae
- Superficial ulceration of mucous membrane limited to 1 site
- Cutaneous reaction/rash with at least 1 of the following\*:
  1. elevations of ALT/AST > 2 x baseline but at least 5 x ULN\*
  2. fever  $\geq 38^{\circ}\text{C}$  or 100 F\*
  3. serum sickness-like reaction\*
  4. eosinophil count > 1000/mm^3\*

*\* added by the sponsor.*

A grade 4 cutaneous reaction/rash is defined as:

- Extensive or generalized bullous lesions
- Stevens-Johnson syndrome (SJS)
- Ulceration of mucous membrane involving 2 or more distinct mucosal sites
- Toxic epidermal necrolysis (TEN).

Subjects experiencing a grade 3 or 4 rash or cutaneous event must have their trial medication discontinued and be withdrawn from the trial. Referral to a dermatologist is recommended for these events. Local safety sampling to determine possible liver or systemic abnormalities is recommended. Close clinical follow-up and appropriate medical intervention is recommended for these events; daily follow-up is recommended for 5 days from the onset of the event to monitor for progression of the event.

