##### Determining Severity Grade

If the severity of an AE could fall under either one of 2 grades (e.g., the severity of an AE could be either grade 2 or grade 3), select the higher of the 2 grades for the adverse event.

**Note:** The laboratory normal ranges should be taken into consideration to assign gradings to a laboratory value.

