**Basic Self-care Functions – Adult:** Activities such as bathing, dressing, toileting, transfer/movement, continence, and feeding.

**Basic Self-care Functions – Young Children:** Activities that are age and culturally appropriate (e.g., feeding self with culturally appropriate eating implement).

**Usual Social & Functional Activities – Adult:** Adaptive tasks and desirable activities, such as going to work, shopping, cooking, use of transportation, pursuing a hobby, etc.

**Usual Social & Functional Activities – Young Children:** Activities that are age and culturally appropriate (e.g., social interactions, play activities, learning tasks, etc.).

| CLINICAL  |   |   |   |  |
|---|---|---|---|--|
| PARAMETER   | GRADE 1
MILD   | GRADE 2
MODERATE   | GRADE 3
SEVERE   | GRADE 4
POTENTIALLY LIFE-
THREATENING  |
| Pruritis associated with injection
See also Skin: Pruritis (itching - no skin lesions)                       | Itching localized to injection site AND Relieved spontaneously or with < 48 hours treatment       | Itching beyond the injection site but not generalized OR Itching localized to injection site requiring ≥ 48 hours treatment | Generalized itching causing inability to perform usual social & functional activities   | NA   |
| SKIN – DERMATOLOGICAL   |   |   |   |  |
| Alopecia  | Thinning detectable by study participant (or by caregiver for young children and disabled adults) | Thinning or patchy hair loss detectable by health care provider   | Complete hair loss  | NA   |
| Cutaneous reaction/rash   | Localized macular rash  | Diffuse macular, maculopapular, or morbilliform rash OR Target lesions  | Diffuse macular, maculopapular, or morbilliform rash with vesicles or limited number of bullae OR Cutaneous reaction/rash with superficial ulcerations of mucous membrane limited to 1 site a OR Cutaneous reaction/rash with at least 1 of the following a : elevation of AST and/or ALT > 2 x baseline but at least > 5 x ULN a ; fever (> 38°C or 100°F) a ; eosinophils > 1000/mm 3a ; serum sickness-like reaction a | Extensive or generalized bullous lesions OR Stevens-Johnson syndrome (SJS) OR Ulceration of mucous membrane involving 2 or more distinct mucosal sites OR Toxic epidermal necrolysis (TEN) |
| Hyperpigmentation   | Slight or localized   | Marked or generalized   | NA  | NA   |
| Hypopigmentation  | Slight or localized   | Marked or generalized   | NA  | NA   |

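### The fever limit that turns a rash into grade 3, and so forces withdrawal, pairs 38°C with 100°F (38°C is 100.4°F) and uses ≥ in Section 5.5.1 but > in Addendum 2

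*Protocol*

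**What the plan says.** Protocol Section 5.5.1 introduces its rash grades with "The following grades are based on the DAIDS grading table" and adds that the sponsor has adapted them. Its list of grade 3 features includes fever at or above 38°C or 100 F, marked as a sponsor addition. The cutaneous reaction/rash row of Addendum 2 (Section 7.2) has the same feature as "fever (> 38°C or 100°F", with a footnote marking it as revised by the sponsor. The two entries therefore state one sponsor criterion.

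The grade determines what happens to the subject:

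- Lower grades: "Subjects experiencing a grade 1 or 2 rash or cutaneous event may continue treatment".
- Grade 3 or 4, Section 5.5.1: "Subjects experiencing a grade 3 or 4 rash or cutaneous event must have their trial medication discontinued and be withdrawn from the trial".
- Section 5.2.5 lists, among the conditions that require withdrawal, that "they experience a grade 3 or higher rash".
- The rash visit schedules in Addenda 4 and 5 make the stop at grade 3 or 4 permanent and rule out rechallenge.

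**The concern.** A stopping rule needs one threshold. This one has two figures that look like a unit conversion and are not, and its operator changes between the section that investigators follow and the table that defines the grades. A site's choice of unit or section can decide whether a subject with a rash and a low-grade fever keeps etravirine.

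Either error has a cost. The trial supplies the drug to people who cannot get it any other way, so an unintended withdrawal works against its stated objective. An unintended continuation leaves a subject on the drug after what the sponsor may have meant to class as a severe reaction.

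**Working it through.** **Inputs.** Section 5.5.1: ≥ 38°C or 100 F. Addendum 2, rash row: > 38°C or 100°F. Addendum 2, nonaxillary fever row: grade 1 is 37.7 to 38.6°C.

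**Does the printed pair reproduce?** With F = C × 9/5 + 32, 38 × 9/5 + 32 = 100.4°F, not 100°F. In the other direction, C = (F − 32) × 5/9 gives (100 − 32) × 5/9 = 37.78°C, not 38°C. The gap is 100.4 − 100 = 0.4°F, or 38.00 − 37.78 = 0.22°C. The pair does not reproduce in either section.

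**What the gap does to one-decimal Celsius readings.** The last three columns show whether a rash with that temperature meets the fever criterion.

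| Reading (°C) | In °F | 100°F figure | ≥ 38°C (5.5.1) | > 38°C (Addendum 2) |
|---|---|---|---|---|
| 37.7 | 99.86 | no | no | no |
| 37.8 | 100.04 | yes | no | no |
| 37.9 | 100.22 | yes | no | no |
| 38.0 | 100.40 | yes | yes | no |
| 38.1 | 100.58 | yes | yes | yes |

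The 100°F column is the same whether that figure is read as ≥ or >, because no one-decimal Celsius reading equals exactly 100°F.

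**Readings in dispute.** 37.8 and 37.9°C differ between units in both sections. 38.0°C differs between sections for a site that uses only the Celsius figure.

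**For scale.** The grade 1 fever row covers ten one-decimal readings (37.7 to 38.6°C). With a rash present, nine of them give grade 3 by the 100°F figure (37.8 to 38.6), seven by ≥ 38°C (38.0 to 38.6) and six by > 38°C (38.1 to 38.6). So 9 − 7 = 2 readings turn on the unit and 7 − 6 = 1 on the operator. These are counts of thermometer steps, not of subjects, and the steps are not equally likely to occur.

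**A smaller mismatch in the same criterion set.** The ALT/AST boundary is at least 5 × ULN in Section 5.5.1 but strictly above 5 × ULN in the Addendum 2 rash row. The table's own ALT and AST rows start grade 3 above 5.0 × ULN. This is editorial.

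**The case against.** The strongest reply is that the text, read literally, is not ambiguous. The two figures are joined by *or*, so the lower one governs. A site that applies either line in full reaches the same grade at every one-decimal Celsius reading, including 38.0°C. Addendum 2 also has a tie-break for an event that could fall under two grades: "select the higher of the 2 grades for the adverse event". That settles most borderline cases on the cautious side.

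This narrows the conflict but does not make the text correct. If 100°F is the working limit, the 38°C figure does nothing except mislead a site that works in Celsius. If 38°C was intended, 100°F is wrong, and the literal reading and the tie-break both send subjects to withdrawal below the intended limit. The tie-break does not say which limit the sponsor meant.

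The second reply concerns reach. Under Amendment 3, for ongoing subjects "the next planned visit will be a Final/Withdrawal Visit, which will be the last visit with data collection". After data collection ends, Section 5.5 says "toxicity management will be performed per local standard of care". Even before then, management is at the investigator's discretion, taking the protocol procedures into account. This stands as a limit. However, Section 5.2.5 includes the switching criterion that goes with the Amendment 3 objective and still requires withdrawal for grade 3 rash, with no exception for the simplified phase. Section 5.2.5 gives no fever figure itself. That the exact limit still binds later is therefore an inference, though a reasonable one.

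A third reply is that the difference in operators could be a text-extraction fault. The 38/100 pairing is the same in both places, so the unit error would remain.

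**Conclusion.** The point holds. The unit pair is wrong in both places, and the operators differ as the text reads. The supported size is 0.4°F (0.22°C), and it matters only for a rash whose sole grade 3 feature is fever. The operator conflict at 38.0°C further requires a site that ignores the Fahrenheit figure.

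The number of subjects affected cannot be estimated, because Flowchart 1 schedules no temperature measurement. No material effect on the SAP tables is claimed.

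The conclusion rests on the two entries being one criterion, which the sponsor markings and the link from Section 5.5.1 to the table support. It merits correction despite its narrow range because it sets the boundary between a rash that may be treated through and a permanent stop.

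**What to change.** State one value, one operator and a correct conversion, identically in Section 5.5.1 and the rash row of Addendum 2. The choices are ≥ 38.0°C (100.4°F) or, if the lower limit was intended, ≥ 37.8°C (100.0°F). The documents do not show which was meant, so the sponsor's medical team should decide. Align the ALT/AST boundary at 5 × ULN in the same edit.

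The cost is a short text change in two protocol sections, with no new data and no change to the SAP. Because it touches a withdrawal criterion, it may be judged substantial. Part II, Section 6.2 would then require IEC/IRB approval before use. It can be included in the next amendment.

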**Basic Self-care Functions – Young Children:** Activities that are age and culturally appropriate (e.g., feeding self with culturally appropriate eating implement).

**Usual Social & Functional Activities – Adult:** Adaptive tasks and desirable activities, such as going to work, shopping, cooking, use of transportation, pursuing a hobby, etc.

**Usual Social & Functional Activities – Young Children:** Activities that are age and culturally appropriate (e.g., social interactions, play activities, learning tasks, etc.)

| LABORATORY  |  |  |  |  |
|---|--|--|--|--|
| PARAMETER   | GRADE 1
MILD  | GRADE 2
MODERATE  | GRADE 3
SEVERE  | GRADE 4
POTENTIALLY
LIFE-
THREATENING   |
| HEMATOLOGY Standard International Units are listed in italics                                   |  |  |  |  |
| Absolute CD4+ count
Adult and Pediatric
> 13 years
(HIV negative only)       | 300 – 400/mm 
300 – 400/μL   | 200 – 299/mm 
200 – 299/μL   | 100 – 199/mm 
100 – 199/μL   | < 100/mm 
< 100/μL  |
| Absolute lymphocyte count
Adult and Pediatric
> 13 years
(HIV negative only) | 600 – 650/mm 
0.600 x 10^9 –
0.650 x 10^9/L                      | 500 – 599/mm 
0.500 x 10^9 –
0.599 x 10^9/L                    | 350 – 499/mm 
0.350 x 10^9 –
0.499 x 10^9/L            | < 350/mm 
< 0.350 x 10^9/L                                    |
| Absolute neutrophil count (ANC)   |  |  |  |  |
| Adult and Pediatric >
7 days  | 1,000 – 1,300/mm 
1.000 x 10^9 –
1.300 x 10^9/L                  | 750 – 999/mm 
0.750 x 10^9 –
0.999 x 10^9/L                    | 500 – 749/mm 
0.500 x 10^9 –
0.749 x 10^9/L            | < 500/mm 
< 0.500 x 10^9/L                                    |

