b Use age and sex appropriate values (e.g., bilirubin), including preterm infants.

c Revised by the sponsor.

d Revised by the sponsor; monomer conversion factor used for conversion from g/dL to mmol/L

| LABORATORY   |  |  |  |   |
|--|--|--|--|---|
| PARAMETER  | GRADE 1
MILD  | GRADE 2
MODERATE  | GRADE 3
SEVERE  | GRADE 4
POTENTIALLY
LIFE-
THREATENING            |
| Infanta,b
22 – 35 days
(HIV positive or
negative ) | 9.5 – 10.5 g/dL
5.8 – 6.4 mmol/L   | 8.0 – 9.4 g/dL
4.8 – 5.7 mmol/L  | 7.0 – 7.9 g/dL
4.2 – 4.7 mmol/L  | < 7.00 g/dL
< 4.2 mmol/L                               |
| Infanta,b
1 – 21 days
(HIV positive or
negative )  | 12.0 – 13.0 g/dL
7.3 – 7.9 mmol/L  | 10.0 – 11.9 g/dL
6.1 – 7.2 mmol/L  | 9.0 – 9.9 g/dL
5.5 – 6.0 mmol/L  | < 9.0 g/dL
< 5.5 mmol/L                                |
| International normalized
ratio of prothrombin time
(INR) c                        | ≥ 1.1 to ≤ 1.5 x ULN   | > 1.5 to ≤ 2.0 x ULN   | > 2.0 to ≤ 3.0 x ULN   | > 3.0 x ULN   |
| Methemoglobin  | 5.0% – 10.0%   | 10.1% – 15.0%  | 15.1% – 20.0%  | > 20.0%   |
| Prothrombin time (PT) d,c   | ≥ 1.1 to ≤ 1.25 x ULN  | > 1.25 to ≤ 1.50 x ULN   | > 1.50 to ≤ 3.00 x ULN   | > 3.00 x ULN  |
| Partial thromboplastin
time (PTT) d  | ≥ 1.1 to ≤ 1.66 x ULN  | > 1.66 to ≤ 2.33 x ULN   | > 2.33 to ≤ 3.00 x ULN   | > 3.00 x ULN  |
| Platelets, decreased   | 100,000 –
124,999/mm 
100,000 x 10^9 –
124,999 x 10^9/L | 50,000 –
99,999/mm 
50,000 x 10^9 –
99,999 x 10^9/L | 25,000 –
49,999/mm 
25,000 x 10^9 –
49,999 x 10^9/L | < 25,000/mm 
< 25,000 x 10  /L |
| WBC, decreased   | 2,000 – 2,500/mm 
2,000 x 10^9 –
2,500 x 10^9/L            | 1,500 – 1,999/mm 
1,500 x 10^9 –
1,999 x 10^9/L        | 1,000 – 1,499/mm 
1,000 x 10^9 –
1,499 x 10^9/L        | < 1,000/mm 
< 1,000 x 10  /L   |
| CHEMISTRIES Standard International Units are listed in italics                       |  |  |  |   |

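### In the grading table, the SI cut-offs for low platelets and low white cells repeat the /mm³ numerals, so the two unit lines in all 8 cells differ by a factor of 1,000 and must be reconciled (minor)

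*Protocol*

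**What the plan says.** Protocol Section 7.2 (Addendum 2) is the scale on which adverse events are graded in this trial. Its haematology rows give each cut-off twice, per mm³ and in SI units.

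- **Platelets, decreased.** Grade 4 is "< 25,000/mm 3 < 25,000 x 10 9 /L". Grade 1 is 100,000 to 124,999/mm³, with the SI line "100,000 x 10 9 – 124,999 x 10 9 /L".
- **WBC, decreased.** Grade 4 is "< 1,000/mm 3 < 1,000 x 10 9 /L". Grade 1 is 2,000 to 2,500/mm³, with the SI line "2,000 x 10 9 – 2,500 x 10 9 /L".
- **Neutrophils, older than 7 days.** Grade 1 is 1,000 to 1,300/mm³, with the SI line "1.000 x 10 9 – 1.300 x 10 9 /L". Grade 4 is "< 500/mm 3 < 0.500 x 10 9 /L".

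Section 5.2.5 uses the grades. Mandatory withdrawal applies if "they experience a grade 4 AE or grade 4 laboratory toxicity considered at least possibly related to ETR by the investigator". Among the exceptions to optional withdrawal for a grade 3 event are "subjects who experience grade 3 absolute neutrophil count or asymptomatic grade 3 platelets". SAP Section 7.3 lists a table (TSFAE04) and a listing (LSFAE02) of grade 3–4 adverse events.

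**The concern.** Two lines in one cell should describe the same count. In the platelet and WBC rows they do not, although other rows of the same table are converted properly. A grader working from a laboratory report in ×10⁹/L would reach a different grade from a grader working in /mm³.

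The harder case to catch is a truly low count. An asymptomatic platelet count that is grade 3 on the /mm³ line falls under an exception in Section 5.2.5. On the SI line the same count is grade 4 and, if considered related, comes under mandatory withdrawal. The table's general instructions also say to take the higher grade when severity could fall under either of two. That instruction is not written for conflicting units, but a grader who applied it here would be pushed towards grade 4.

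**Working it through.** **Inputs.** All cut-offs come from Protocol Section 7.2, Addendum 2. The only outside fact is the unit identity 1 L = 10⁶ mm³.

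**Formula.** x/mm³ = x × 10⁶/L = (x/1,000) ×10⁹/L.

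**Step 1: rows where the printed SI figure is reproduced.** The formula was applied to the grade 1–3 limits of the lymphocyte row and the three neutrophil age bands (4 rows × 6 limits = 24). For example, 1,000/mm³ gives 1.000, 1,300/mm³ gives 1.300 and 599/mm³ gives 0.599 ×10⁹/L. All 24 printed values match (ratio of printed to computed = 1.0).

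**Step 2: platelet and WBC rows.**

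| Row, grade | /mm³ line | Same count in ×10⁹/L | Printed SI line | Ratio |
|---|---|---|---|---|
| Platelets 1 | 100,000–124,999 | 100.000–124.999 | 100,000–124,999 | 1,000 |
| Platelets 2 | 50,000–99,999 | 50.000–99.999 | 50,000–99,999 | 1,000 |
| Platelets 3 | 25,000–49,999 | 25.000–49.999 | 25,000–49,999 | 1,000 |
| Platelets 4 | < 25,000 | < 25.000 | < 25,000 | 1,000 |
| WBC 1 | 2,000–2,500 | 2.000–2.500 | 2,000–2,500 | 1,000 |
| WBC 2 | 1,500–1,999 | 1.500–1.999 | 1,500–1,999 | 1,000 |
| WBC 3 | 1,000–1,499 | 1.000–1.499 | 1,000–1,499 | 1,000 |
| WBC 4 | < 1,000 | < 1.000 | < 1,000 | 1,000 |

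The third column is the arithmetic equivalent of the second. It shows the size of the conflict and is not a proposed threshold.

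**Step 3: what the SI line does if read literally.**

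- Platelets 125,000/mm³ = 125 ×10⁹/L. No grade on the /mm³ line; 125 < 25,000, so grade 4 on the SI line.
- Platelets 30,000/mm³ = 30 ×10⁹/L. Grade 3 on the /mm³ line; 30 < 25,000, so grade 4 on the SI line.
- WBC 2,501/mm³ = 2.501 ×10⁹/L. No grade on the /mm³ line; 2.501 < 1,000, so grade 4 on the SI line.

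The highest graded counts on the /mm³ lines (124,999 platelets and 2,500 white cells, or 124.999 and 2.5 ×10⁹/L) lie below the SI grade 4 cut-offs. So every count that is grade 1, 2 or 3 on the /mm³ line is grade 4 on the SI line.

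**Step 4: is it a decimal comma?** If the comma is read as a decimal mark in the SI lines only, every ratio becomes 1.0. But the line above in the same cell uses the comma for thousands. The neutrophil rows use the point for decimals, and so does the proteinuria row (1,000–1,999 mg/24 h shown as 1.000–1.999 g/d).

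**The case against.** The strongest reply is that this is one punctuation mark with almost no route to a subject or to the data. Most of that stands.

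- **Cause.** A comma printed for a point explains every cell, and the three digits after the mark match the style of the neutrophil rows. A fault in reading the PDF cannot be fully excluded, though a uniform pattern across two rows, with neighbouring rows intact, makes it less likely. Neither row is marked as revised by the sponsor, so the slip may be inherited from the published table; that cannot be checked here.
- **Forced withdrawal.** A reader might infer that a subject with a normal count would have to be withdrawn. The documents do not support this. Section 5.2.5 also requires the investigator to consider the toxicity at least possibly related to etravirine, the grading instructions say that laboratory normal ranges are to be considered, and the /mm³ cut-off is in the same cell. The documents give no normal range either, so the secure statement concerns a count with no grade on the /mm³ line.
- **Distorted safety tables.** A reader might infer that TSFAE04 and LSFAE02 are unreliable. The documents do not support this either. The flowchart and Section 5.4.3.1.1 schedule only a urine pregnancy test, so blood counts would come from local care or unscheduled safety samples. SAP Sections 7.2 and 7.3 plan no laboratory toxicity table. Part II Section 1.4 limits collection to related events, events leading to interruption or discontinuation, and serious events, with others only where local rules require. Once data collection ends, toxicity management follows local standard of care (Sections 5.5 and 5.6).

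Two parts of the reply do not stand. The table's own conventions contradict the decimal-comma reading. And the advice to consider normal ranges does not settle a count such as 30 ×10⁹/L, which is graded on both lines and differs only in the grade.

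**Conclusion.** The contradiction is real and exact: a factor of 1,000 in all 8 cells, in a table that the protocol uses to grade events and that feeds a withdrawal rule. Severity is minor. Nothing in the documents shows that any subject was misgraded, and the routes by which one could be are narrow. The realistic exposure is a low platelet or white-cell count, reported by a local laboratory in ×10⁹/L, that becomes a reportable event and is graded from the SI line.

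The conclusion assumes that the text read from the PDF matches the printed page. Its practical weight also depends on some site laboratories reporting in ×10⁹/L, which the documents do not state. This review takes no view on which line should govern the clinical rule.

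**What to change.** Check the platelet and WBC rows against the source document to rule out a PDF-reading fault. If the cells are printed as read here, reconcile the two unit lines so that both describe the same counts, consistent with the conversion already used in the neutrophil rows. Before the final analysis, identify any reported platelet or white-cell adverse event graded from SI values and confirm that its grade agrees with the reconciled thresholds. The cost is a correction to 8 table cells and a short look at what is likely to be few entries; the SAP outputs do not change.

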| Sodium, serum, high                          | 146 – 150 mEq/L
146 – 150 mmol/L         | 151 – 154 mEq/L
151 – 154 mmol/L     | 155 – 159 mEq/L
155 – 159 mmol/L                                   | ≥ 160 mEq/L
≥ 160 mmol/L                                       |
| Sodium, serum, low                           | 130 – 135 mEq/L
130 – 135 mmol/L         | 125 – 129 mEq/L
125 – 129 mmol/L     | 121 – 124 mEq/L
121 – 124 mmol/L                                   | ≤ 120 mEq/L
≤ 120 mmol/L                                       |
| Triglycerides (fasting)                      | NA   | 500 – 750 mg/dL
5.65 – 8.48 mmol/L   | 751 – 1,200 mg/dL
8.49 – 13.56 mmol/L                              | > 1,200 mg/dL
> 13.56 mmol/L                                |
| Uric acid                                    | 7.5 – 10.0 mg/dL
0.45 – 0.59 mmol/L      | 10.1 – 12.0 mg/dL
0.60 – 0.71 mmol/L | 12.1 – 15.0 mg/dL
0.72 – 0.89 mmol/L                               | > 15.0 mg/dL
> 0.89 mmol/L                                  |

a Values are for term infants.

b Use age- and sex-appropriate values (e.g., bilirubin), including preterm infants.

c Revised by the sponsor.

| LABORATORY   |   |   |   |  |
|---|---|---|---|--|
| PARAMETER  | GRADE 1
MILD                                       | GRADE 2
MODERATE                                   | GRADE 3
SEVERE                                       | GRADE 4
POTENTIALLY
LIFE-
THREATENING |
| URINALYSIS Standard International Units are listed in italics |   |   |   |  |
| Hematuria (microscopic)   | 6 – 10 RBC/HPF  | > 10 RBC/HPF  | Gross, with or without clots OR with RBC casts                  | Transfusion indicated                                    |
| Proteinuria, random collection  | 1 +   | 2 – 3 +   | 4 +   | NA   |
| Proteinuria, 24 hour collection   |   |   |   |  |
| Adult and Pediatric
≥ 10 years                                   | 200 – 999 mg/24 h
0.200 – 0.999 g/d                 | 1,000 – 1,999 mg/24 h
1.000 – 1.999 g/d             | 2,000 – 3,500 mg/24 h
2.000 – 3.500 g/d               | > 3,500 mg/24 h
> 3.500 g/d                           |

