| Pediatric
> 3 months –
< 10 years                      | 201 – 499 mg/m  /24 h
0.201 – 0.499 g/d | 500 – 799 mg/m  /24 h
0.500 – 0.799 g/d | 800 – 1,000 mg/m  /24 h
0.800 – 1.000 g/d | > 1,000 mg/ m  /24 h
> 1.000 sg/d         |

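### In the 24-hour proteinuria row for children under 10, the grading table's g/d line drops the per-m² term, so one result can receive two different grades, including across the grade 4 limit

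*Protocol*

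**What the plan says.** The urinalysis block of the grading table (Protocol Part I, Section 7.2, Addendum 2) says that "Standard International Units are listed in italics". The second line of each cell is therefore offered as a restatement of the line above it.

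For 24-hour proteinuria, age over 3 months to under 10 years, the cells read:

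- Grade 1: 201–499 mg/m²/24 h, with "0.201 – 0.499 g/d" beneath.
- Grade 2: 500–799 mg/m²/24 h, with "0.500 – 0.799 g/d" beneath.
- Grade 3: 800–1,000 mg/m²/24 h, with "0.800 – 1.000 g/d" beneath.
- Grade 4: above 1,000 mg/m²/24 h, with above 1.000 beneath in a unit printed as sg/d.

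The row for age 10 and older is absolute in both lines. Its grade 1 is 200–999 mg/24 h, with "0.200 – 0.999 g/d" beneath.

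Protocol Section 5.2.5 uses the grades. Subjects must be withdrawn if "they experience a grade 4 AE or grade 4 laboratory toxicity considered at least possibly related to ETR by the investigator". They may be withdrawn if "a grade 3 AE (with the exception of skin events / allergic reaction) occurs according to the DAIDS grading scale", subject to listed exceptions. Section 5.2.2 admits children from age 2. SAP Section 7.3 lists TSFAE04, a table of grade 3–4 adverse events whatever their cause.

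**The concern.** Converting milligrams to grams cannot remove a body-surface term. As printed, one line grades protein per square metre and the other grades total protein, yet both carry the same digits. A site whose laboratory reports total g/d and a site that normalises to body surface can grade the same urine collection differently.

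What is at stake is mainly the grade 4 limit. Random-collection proteinuria has no grade 4 in this table, so the 24-hour rows are the only proteinuria rows that can trigger the mandatory-withdrawal item. A smaller matter is whether a reported event counts as grade 3–4 in TSFAE04.

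**Working it through.** **Inputs.** The limits are those of Addendum 2. The weights are chosen from the bands in Table 1 of Protocol Section 5.3.3, which run from 10 kg to 30 kg and over. The documents give no body surface, so it is assumed here as B = (4W+7)/(W+90), with W in kg and B in m².

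**Step 1: reproduce the printed figures.** Dividing by 1,000:

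- Under 10 years: 201→0.201, 499→0.499, 500→0.500, 799→0.799, 800→0.800, 1,000→1.000. Every digit reproduces, but the unit that results is g/m²/d, not g/d.
- 10 years and older, as a control: 200→0.200, 999→0.999. Digits and unit both reproduce.

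**Step 2: when do the two lines agree?** Let E be the excretion in mg/24 h. The upper line compares E/B with the limits 201, 500, 800 and 1,000. The lower line compares E itself with the same limits. They agree at every value only if B = 1.0 m². With the assumed formula, 4W+7 = W+90 gives W = 83/3 = 27.7 kg.

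**Step 3: the g/d grade 4 limit expressed per m².** This is 1,000/B:

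| Weight | B | 1.000 g/d equals |
|---|---|---|
| 10 kg | 47/100 = 0.470 m² | 2,128 mg/m²/24 h |
| 15 kg | 67/105 = 0.638 m² | 1,567 mg/m²/24 h |
| 20 kg | 87/110 = 0.791 m² | 1,264 mg/m²/24 h |
| 30 kg | 127/120 = 1.058 m² | 945 mg/m²/24 h |

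**Step 4: two children.**

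- 15 kg at 1,100 mg/m²/24 h: 1,100 × 0.638 = 702 mg, or 0.70 g/d. The upper line gives grade 4, the lower line grade 2.
- 30 kg at 970 mg/m²/24 h: 970 × 1.058 = 1,026 mg, or 1.03 g/d. The upper line gives grade 3, the lower line grade 4.

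**Step 5: the same check without the formula.** The table shows, for a plain range of B, the excretions (whole mg/24 h) at which exactly one line gives grade 4:

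| B | Excretion | Line giving grade 4 |
|---|---|---|
| 0.45 m² | 451–1,000 | mg/m² line |
| 0.6 m² | 601–1,000 | mg/m² line |
| 0.8 m² | 801–1,000 | mg/m² line |
| 1.0 m² | none | – |
| 1.2 m² | 1,001–1,200 | g/d line |

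The lower limits are affected too: 400 mg/24 h at 0.6 m² is 667 mg/m²/24 h, grade 2 by the upper line and grade 1 by the lower. If both lines carried the same normalisation, no value would be graded differently at any B.

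**The case against.** The case against giving this much weight is strong.

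- **The trial does not schedule the test.** Neither flowchart includes urine protein, and the only laboratory test specified in Section 5.4.3.1.1 is the urine pregnancy test. This stands: the row matters only when a site orders a 24-hour collection locally in a child under 10.
- **Withdrawal is conditional.** A grade 4 value alone does not require it, because the investigator must also see at least a possible link to etravirine. This stands.
- **The table has a tie-break.** Its general instructions tell the grader to take the higher grade when two could apply. That helps someone who works through both lines. A site that reads only the g/d line sees one grade and no tie.
- **Local care takes over.** After data collection ends, Sections 5.5 and 5.6 leave toxicity management to local standard of care. Section 5.2.5 contains no such release. Its Amendment 3 sentence concerns only how termination is recorded, so the withdrawal item remains in force on paper.
- **The mismatch may be inherited.** The row is not marked as revised by the sponsor, and its origin cannot be checked from the documents. The protocol nevertheless adopts the table for adverse event reporting.
- **The sg/d unit may be a typing or text-reading slip.** Nothing here depends on it.

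**Conclusion.** The two unit lines contradict each other in all four grades of this row. They are equal only at 1.0 m², and the difference can cross the grade 4 limit. That follows from the printed units alone. The worked sizes rest on the assumed body-surface formula, or on the plain range of 0.45 to 1.2 m². The conditional withdrawal rule can touch any child under 10 on study, including those entering under Amendment 3.

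A reader might infer two stronger points that the documents do not support:

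- **That the g/d line is always the more lenient one.** The direction reverses above 1.0 m², as the 30-kg case shows.
- **That the youngest children, where the gap is widest, distort TSFAE04.** Children entering under Amendment 3 are documented in medical records only (Section 5.1.1), and no statistical analysis follows the end of CRF collection (Section 5.7.3). Any effect on TSFAE04 is confined to children under 10 with CRF data. Even then, Part II Section 1.4 collects an event only if it is serious, possibly related or leads to interruption or discontinuation, unless local regulations require more.

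Severity is minor. How often 24-hour collections are done is not stated, so the number of affected children cannot be estimated.

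**What to change.** Reconcile the two lines in all four cells of this row so that they express the same limits in the same normalisation. The sponsor should confirm which is intended: the choice fixes a limit used in a withdrawal rule, and this review does not make it. Correct the grade 4 unit at the same time. Then recheck any pediatric proteinuria event already graded from this row against the confirmed unit.

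The cost is four table cells and a short search of the pediatric adverse event records. No analysis method or data collection changes.
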